9. STATISTICAL DESIGN AND ANALYSIS

This section describes the statistical considerations and analysis plans for the EXCEL trial. The study is powered for both the primary and the 2 major secondary endpoints through an anticipated median follow-up of three years.

In general, binary variables will be summarized using counts, percentages, and exact 95% confidence intervals. For continuous variables, percentiles, means, standard deviations, and 95% confidence intervals for the mean using the Gaussian approximation will be calculated. Time to event data will be summarized using Kaplan-Meier estimates and 95% confidence intervals. Kaplan-Meier curves will be constructed for the primary and major secondary endpoints and differences in treatment will be tested using the difference in Kaplan-Meier failure rates on all available data through 3-year follow-up at the time of the analysis (event driven analysis). All primary analyses will be measured from randomization onward and will be by intention to treat according to randomized assignment, regardless of what therapy was actually received. A sensitivity analysis will be performed on the primary endpoint defined from the index procedure date. The composite of all-cause mortality, MI, stroke (mRS \geq 1 and increase by \geq 1 from baseline), or unplanned revascularization for ischemia at 3 years post randomization will also be classified as a sensitivity analysis. Secondary analyses will be performed for the per protocol (PP) population (see also Section 9.1.5.2).

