H_A: $F_{COMP-PCI}(T) - F_{COMP-CABG}(T) < \Delta_{COMP}$.

 $F_{COMP-PCI}(T) - F_{COMP-CABG}(T)$ is the difference in failure rates at 3 years between CABG and PCI and Δ_{COMP} is the non-inferiority margin for this powered secondary endpoint.

Assuming the following:

- major secondary endpoint event rate is 22% in each treatment arm at 3 years (using 3-year event rates from the SYNTAX trial)
- median time to follow-up is approximately 3 years
- minimum time to follow-up is 2 years
- 8% lost to follow-up at 3 years
- non-inferiority $\Delta_{\text{COMP}} = 8.4\%$
- one-sided alpha = 0.05
- accrual time of 29 months

then a sample size of 1900 subjects (~950 per arm) will provide an approximately 99% power to demonstrate non-inferiority of CABG to PCI using the Com-Nougue approach.

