9.1.7. Statistical Analysis

9.1.7.1. Analysis of Primary and Major Powered Secondary Endpoints

The primary and the two major powered secondary endpoints will be analyzed for the intentto-treat population, the as-treated population and the per-protocol population. Formal hypothesis testing will be based on the intent-to-treat population. Hierarchical testing will be employed following the order below:

- Primary endpoint-All cause mortality, MI or Stroke from randomization to median follow-up of 3 years (non-inferiority)
- First major powered secondary endpoint-All cause mortality, MI or Stroke from randomization to 30 days
- Second major powered secondary endpoint-All cause mortality, MI, Stroke or Unplanned Revascularization for Ischemia from randomization to median of 3 years
- Primary endpoint All cause mortality, MI, or stroke from randomization to median follow-up of 3 years (superiority)

Formal hypothesis testing of the first major powered secondary endpoint will occur only if noninferiority for the primary endpoint is met. Simultaneous formal hypothesis testing of the second major powered secondary endpoint and the superiority test of the primary endpoint will occur only if non-inferiority for the first major powered secondary endpoint is met.

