2.3 DESIGN OF THE STUDY

The randomized control portion of this study (that will be referred to as RCT) is a prospective, unblinded, randomized multicenter trial of approximately 1,900 subjects enrolled at approximately 165 US and OUS centers. Following diagnostic angiography demonstrating significant ULMCA disease and consensus of the local Heart Team (qualified participating interventional cardiologist and cardiac surgeon) that the subject meets the study entry criteria, subjects will be consented and randomized 1:1 to: a) PCI using XIENCE (N=950), or b) CABG (N=950). Follow-up for all randomized subjects will continue for five years with a potential for additional follow-up to 10 years. The primary endpoint will be assessed at least 2-years after the last subject is randomized, with a median follow-up duration in all subjects of at least 3 years.

All randomized subjects will have a follow-up telephone contact or office visit at 30 days, 180 days, and 1, 2, 3, 4 and 5 years following the index procedure. In addition, to minimize bias in the assessment of the primary endpoint, at the time the last randomized subject reaches the 2-year follow-up duration (730 + 28 = 758 days), an additional adverse event (AE) check will be performed in order for data up to 3 years (365 days*3=1095 days) from the date of randomization to be collected equally in both arms.

The AE check will commence the day after the 2-year follow-up duration of the last subject enrolled (i.e. 758 days), and will be completed prior to the database snapshot. At this time,

subjects with either of the following conditions should be contacted by each clinical site by phone or office visit to collect AE information:

- Subjects who have not yet completed the 3-year visit, unless the most recent follow-up was completed within 28 days of the AE check initiation; or
- Subjects who have completed a 3-year visit before day 1067 after randomization (i.e. >28 days prior to exactly 3 years [1095 days]).

For subjects who have completed any follow-up visit at \geq (1095 – 28= 1067) days, the AE check is not required.

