2.5.1 Primary Endpoint

The primary endpoint of all cause death, MI or stroke (mRS \geq 1 and increase by \geq 1 from baseline) occurring up to 3 years post randomization will be evaluated using the difference in Kaplan-Meier failure rates in the intent-to-treat population. For the primary endpoint, sample size calculations for the Com-Nougue approach¹, which utilizes the difference in Kaplan-Meier failure rate estimates, were derived using simulations. The Com-Nougue approach was very similar to that calculated using the asymptotic approach (difference \leq 0.5%). Therefore, the asymptotic test was used to approximate the power for the Com-Nougue approach using PASS 2008 (NCSS, LLC. Kaysville, Utah)³.

The hypothesis test is designed to show non-inferiority of PCI to CABG for the primary endpoint via the Z statistic, which is a normal approximation to the Binomial, with a one-sided alpha of 0.025. The null (H_0) and alternative (H_A) hypotheses are:

```
H0: F_{PCI-PE}(T) - F_{CABG-PE}(T) \ge \Delta_{PE}
```

```
HA: F_{PCI-PE}(T) - F_{CABG-PE}(T) < \Delta_{PE}.
```

 F_{PCI-PE} and $F_{CABG-PE}$ are the Kaplan-Meier estimates of failure rate of the primary endpoint at 3 years in the PCI and CABG arms, respectively. Δ_{PE} is the non-inferiority margin for the primary endpoint.

The sample size calculation is based on the following assumptions:

- primary endpoint event rate is 11% in each treatment arm at 3 years (using 3-year event rates from the SYNTAX trial, the most contemporary reference dataset)
- minimum time to follow-up is 2 years
- median time to follow-up is approximately 3 years
- 8% lost to follow-up at 3 years
- non-inferiority margin $\Delta_{\text{PE}} = 4.2\%$
- one-sided alpha = 0.025
- accrual time of 29 months.

A sample size of 1,900 subjects (950 per arm) will provide approximately 80% power to

demonstrate non-inferiority of PCI to CABG.

If non-inferiority is met, superiority testing will be performed with a one-sided alpha of 0.025. The null (H_0) and alternative (H_A) hypotheses for the superiority test are:

H₀: $F_{PCI-PE}(T) - F_{CABG-PE}(T) \ge 0$

H_A: $F_{PCI-PE}(T) - F_{CABG-PE}(T) < 0$.

Using a one-sided alpha of 0.025, assuming 8% lost to follow-up at 3 years, the trial will have approximately 80% power to demonstrate superiority with a difference of 3.84% of PCI to CABG (e.g. 7.16% in the PCI arm vs. 11% in the CABG arm).

2.5.2 Major Powered Secondary Endpoints:

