The first major powered secondary endpoint is defined as the composite of all cause death, MI, or stroke (mRS \geq 1 and increase by \geq 1 from baseline) occurring up to 30 days post randomization. It will be evaluated using the difference in Kaplan-Meier rates tested using the Com-Nougue approach¹ which is similar to the normal approximation to the binomial. The null (H₀) and alternative (H_A) hypotheses for non-inferiority of this major secondary endpoint is:

H₀: $F_{PCI-PE30}(T) - F_{CABG-PE30}(T) \ge \Delta_{PE30}$

H_A: $F_{PCI-PE30}(T) - F_{CABG-PE30}(T) < \Delta_{PE30.}$

 $F_{PCI-PE30}(T)$ - $F_{CABG-PE30}(T)$ is the difference in Kaplan-Meier rates at 30 days between PCI and CABG arms and Δ_{PE30} is the non-inferiority margin for this powered secondary endpoint.

The power calculation is based on the following assumptions:

- composite event rate is 3% in each treatment arm at 30 days
- non-inferiority margin $\Delta_{\text{PE30}} = 2\%$
- one-sided alpha = 0.05

A sample size of 1,900 subjects (950 per arm) will provide approximately 80% power to demonstrate non-inferiority of PCI to CABG.

The second major powered secondary endpoint is defined as the composite of all cause death, MI, stroke, or unplanned revascularization for ischemia occurring by 3 years post randomization. This composite will be evaluated using the difference in Kaplan-Meier failure rates at 3 years between CABG and PCI in all 3 patient populations. The hypothesis is designed to show non-inferiority of PCI to CABG with a one-sided alpha of 0.05. The null (H₀) and alternative (H_A) hypotheses for non-inferiority of this powered secondary endpoint are:

H₀: $F_{COMP-PCI}(T) - F_{COMP-CABG}(T) \ge \Delta_{COMP}$ H_A: $F_{COMP-PCI}(T) - F_{COMP-CABG}(T) < \Delta_{COMP}$. $F_{COMP-PCI}(T) - F_{COMP-CABG}(T)$ is the difference in failure rates at 3 years between CABG and PCI and Δ_{COMP} is the non-inferiority margin for this powered secondary endpoint.

The power calculation is based on the following assumptions:

- composite event rate is 22% in each treatment arm at 3 years
- minimum time to follow-up is 2 years
- median time to follow-up is approximately 3 years
- 8% lost to follow-up at 3 years
- non-inferiority margin $\Delta_{\text{COMP}} = 8.4\%$
- one-sided alpha = 0.05
- accrual time of 29 months

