A sample size of 1,900 subjects (950 per arm) will provide approximately 99% power to demonstrate non-inferiority of PCI to CABG using the Z statistic from the Com-Nougue approach¹, which is similar to the normal approximation to the Binomial.

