3.10 MULTIPLICITY ISSUES

If EXCEL has met the primary analyses of its primary endpoint of the non-inferiority test on the ITT population, additional hypothesis tests for the of the powered secondary endpoints based on the ITT population will be performed following a fixed sequence as below (FWER=family wise error rate). All of these analyses will be performed from time from randomization:

Step 1: Family 1. Primary Endpoint: Death/MI/Stroke at 3 Years PCI non-inferior to CABG (one-sided alpha of 0.025) If passed non-inferiority, PROCEED to Step 2
If failed non-inferiority, STOP

Step 2: Family 2. Major Secondary Endpoint 1: Death/MI/Stroke at 30 Days PCI non-inferior to CABG

(one-sided alpha of 0.05)

If passed non-inferiority, PROCEED to Step 3
If failed non-inferiority, STOP

Step 3: (Simultaneous Testing of 3-1 and 3-2) 3-1. Family 1. Primary Endpoint: Death/MI/Stroke at 3 Years PCI superior to CABG (one-sided alpha of 0.025) 3-2. Family 3. Major Secondary Endpoint 2: Death/MI/Stroke/Revascularization at 3 Years PCI non-inferior to CABG

(one-sided alpha of 0.05)

For hypothesis test(s) of each of the major powered secondary endpoints, the type I error is a 1sided alpha of 0.05. If any hypothesis testing fails in steps 1 and 2, no further testing for the following step will be performed for labeling purposes. However they will still be tested for research and publication purposes. For example, if PCI failed to show non-inferiority to CABG for the major power secondary endpoint of Death/MI/Stroke at 30 Days (step 2), then the hypothesis in step 3 will not be tested for labeling purposes, but may be tested for exploratory reasons. Caution must be exercised when interpreting p-values displayed for analyses other than those performed for the primary and key powered secondary endpoints, as the study was not powered to detect differences on any of those other variables. The resulting p-values, whether or not less-than 0.05, may be a result simply due to chance, and are displayed for hypothesisgenerating purposes only.

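### The stated power for the two major secondary endpoints (about 80% and 99%) ignores the testing order; under the written sequence, a formal claim on either has about 70% power

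*SAP*

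**What the plan says.** SAP 2.5.2 and Protocol 9.1.6.2 work out power for each major secondary endpoint from that endpoint's own rate, margin and alpha.

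- **30 days (death, MI, stroke).** The SAP assumes "composite event rate is 3% in each treatment arm at 30 days", a 2% margin and one-sided alpha 0.05. Stated power is about 80%.
- **3 years (death, MI, stroke, unplanned revascularization).** The assumptions are 22% in each arm, an 8.4% margin, one-sided alpha 0.05 and 8% loss. The SAP states "A sample size of 1,900 subjects (950 per arm) will provide approximately 99% power to demonstrate non-inferiority of PCI to CABG"; the Protocol likewise says the sample size "will provide an approximately 99% power to demonstrate non-inferiority".

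The opening of Protocol section 9 adds: "The study is powered for both the primary and the 2 major secondary endpoints through an anticipated median follow-up of three years".

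The decision rule is set elsewhere. Protocol 9.1.7.1 says: "Formal hypothesis testing of the first major powered secondary endpoint will occur only if noninferiority for the primary endpoint is met". It then allows formal testing of the composite, together with superiority on the primary endpoint, only after 30-day non-inferiority. SAP 3.10 sets the same three-step sequence: "If any hypothesis testing fails in steps 1 and 2, no further testing for the following step will be performed for labeling purposes". Its next sentence says the tests will still be done for research and publication.

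On superiority, SAP 2.5.1 gives "approximately 80% power to demonstrate superiority with a difference of 3.84% of PCI to CABG". There, in Protocol 9.1.6.1 and in the Protocol synopsis, the superiority test follows once primary non-inferiority is met, with no mention of the 30-day endpoint.

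**The concern.** A claim that depends on passing other tests first cannot be more likely than passing those tests. The composite stands behind two gates, each with power close to 80%, yet its power is printed as 99%. The 30-day endpoint stands behind one such gate, yet its power is printed as if there were none.

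A reader who takes the printed figures with the statement that the study is powered for both secondaries would think a formal result on the composite almost assured. Protocol 9.1.6.2 says that this endpoint exists to allow direct comparison with the SYNTAX trial. At stake is an accurate statement of how often the design, as written, can support a formal claim on each secondary. Type I error, the estimates and the primary conclusion are not in question.

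**Working it through.** **Inputs.** All come from SAP 2.5.1 and 2.5.2, and the Protocol agrees: 950 per arm; primary rate 11% in each arm at 3 years, margin 4.2%, one-sided alpha 0.025; 30-day rate 3%, margin 2%, alpha 0.05; composite rate 22%, margin 8.4%, alpha 0.05; 8% loss at 3 years, so 950 × 0.92 = 874 per arm for the 3-year endpoints. Protocol 9.1.6.2 treats loss at 30 days as minimal, so 950 per arm is used there.

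**Step 1: reproduce the printed figures.** For equal true rates p, power = Φ(margin / √(2p(1−p)/n) − z).

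- Primary non-inferiority: 0.042 / √(2 × 0.11 × 0.89 / 874) − 1.960 gives 80.1% (printed: about 80%).
- 30-day non-inferiority: 0.02 / √(2 × 0.03 × 0.97 / 950) − 1.645 gives 81.9% (printed: about 80%).
- Composite non-inferiority: 0.084 / √(2 × 0.22 × 0.78 / 874) − 1.645 gives 99.5% (printed: about 99%).
- Superiority, 7.16% vs 11%: 0.0384 / √((0.0716 × 0.9284 + 0.11 × 0.89) / 874) − 1.960 gives 80.0% (printed: about 80%).

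All four reproduce, so the printed figures are for single, ungated tests.

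**Step 2: a bound that needs no model.** A formal claim on either secondary requires primary non-inferiority. Its probability therefore cannot exceed 80.1%, whatever the correlations.

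**Step 3: joint power.** The endpoints are nested: events by 30 days are among those by 3 years, which are among the composite events. With equal n, the correlation of the 30-day and 3-year statistics is

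0.03 × 0.89 / √(0.03 × 0.97 × 0.11 × 0.89) = 0.50.

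With 950 patients at 30 days and 874 at 3 years it is 0.50 × √(874/950) = 0.48. The other two correlations, found the same way, are 0.66 (3-year with composite) and 0.32 (30-day with composite). The multivariate normal probabilities are:

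| Formal claim | Tests that must pass | Stand-alone | Gated |
|---|---|---|---|
| 30-day endpoint | primary, 30-day | 81.9% | 69.9% |
| Composite | primary, 30-day, composite | 99.5% | 69.8% |

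Once both gates are passed the composite almost always passes too, so its gated power is nearly that of the two gates.

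**Step 4: sensitivity.**

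- Correlation between the 30-day and 3-year statistics: the two gates pass together in 0.801 × 0.819 = 65.6% if independent, 70.1% at correlation 0.5 and 73.3% at 0.75.
- Simulation with the Kaplan-Meier difference over the Greenwood standard error, uniform accrual over 29 months, 2-year minimum follow-up and 8% loss: 69.2% for each claim in 10,000 trials; 68.2% and 68.1% in a separate run of 6,000.
- The same simulation with loss only and no staggered follow-up: 71.8% and 71.7%.

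**Step 5: superiority if the 30-day gate applies.** At 7.16% vs 11% the primary non-inferiority gate is passed almost always, so only the 30-day gate matters. The plan gives no 30-day rates for this scenario. With CABG at 3%, joint power is 70.4% if PCI is also 3%, 78.1% at 2.5% and 79.8% at 2.0%. A PCI rate lowered in proportion (3% × 7.16/11 = 1.95%) also gives about 80%.

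**The case against.** The strongest reply is that no printed number is wrong. Each is given beside its own rate, margin and alpha; the SAP ties the 99% to the Z statistic of that test; and marginal power per endpoint is common practice. That stands: a reader might infer a calculation error, and there is none. What does not stand is leaving the figures unqualified when another section of the same plan withholds the formal test in about 3 trials in 10 (100% − 69.8% = 30.2%).

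Second, SAP 3.10 limits the stop to labeling and keeps the tests for research and publication. For a published comparison with SYNTAX outside the sequence, about 99% remains the right figure. This limits the point to formal claims. It does not remove it, because Protocol 9.1.7.1 makes formal testing conditional with no such exception.

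Third, a reader might infer that superiority power also falls to about 70%. The documents do not support that as a general figure. It needs 3% in both arms at 30 days, which the plan assumes only for the non-inferiority case. It would place all of PCI's advantage after day 30 (7.16 − 3 = 4.16% vs 11 − 3 = 8%), although Protocol 9.1.6.1 and SAP 2.6 expect lower peri-procedural morbidity and fewer early strokes with PCI. If superiority follows primary non-inferiority alone, as SAP 2.5.1 reads, the 80% stands.

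Fourth, the sample size was set for the primary endpoint (SAP 2.5), and SAP 2.7 defines study success by that test alone. That is correct, and it is why the remedy is only wording.

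**Conclusion.** The concern holds for the two major secondary endpoints. As powers of the written decision rule, the stated figures are too high: for a formal claim, about 70% against about 80% printed for the 30-day endpoint, and about 70% against about 99% for the composite. The result rests on the plan's own rates, margins, alphas and sample size. The one quantity the plan does not give, the correlation between the 30-day and 3-year statistics, moves it between about 66% and 73% over correlations of 0 to 0.75. The ceiling of about 80% for the composite needs no such assumption.

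For superiority the finding is narrower: the documents describe two different conditions for the test. If the 30-day gate applies, power runs from about 70% to about 80%, depending on a PCI 30-day rate that the plan does not state.

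It would be wrong to conclude that the trial is too small or that study success is less likely than stated. Primary non-inferiority keeps its roughly 80%.

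**What to change.** - **SAP 2.5.2 and Protocol 9.1.6.2:** keep the printed 80% and 99%, label them as marginal power that ignores the testing order, and add that power for a formal claim under the fixed sequence is about 70% for each endpoint at the assumed rates.
- **Protocol section 9, opening paragraph:** qualify the statement that the study is powered for both secondaries in the same way.
- **Same places:** say that the lower figures concern formal (labeling) claims only, that the tests will still be run for research and publication, and that study success is unaffected.
- **Superiority:** reconcile the synopsis, Protocol 9.1.6.1 and SAP 2.5.1 with Protocol 9.1.7.1 and SAP 3.10 on whether 30-day non-inferiority is required first. If it is, state the 30-day rates assumed and give gated power as about 70% (PCI 3%) to about 80% (PCI 2% or lower).

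The cost is wording in two documents and one short calculation or simulation. The stated power becomes less favourable. Sample size, testing order and alpha do not change.

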2.6 JUSTIFICATION OF DELTA

The non-inferiority margin of 4.2% for the primary endpoint is for the difference between the cumulative event rates at 3 years. For the PCI arm to pass the non-inferiority test for the primary endpoint of the composite of death, MI and stroke at 3 years, the maximum allowable event rate would be approximately 12.1%. Compared to the 11% event rate of the CABG arm, the average difference per year is approximately 0.4%. The criteria for an acceptable non-inferiority delta was carefully considered by the principal investigators, executive committee, PCI and surgical committees and country leaders of this protocol, representing more than 100 physicians not related to the study sponsor, 50% of whom are interventional cardiologists and 50% of whom are cardiac surgeons. A non-inferiority margin of 4.2% for the primary endpoint in this protocol has been agreed upon by this balanced study leadership to represent clinical therapeutic interchangeability between PCI and CABG, given the substantially lower peri-procedural morbidity of PCI, the likelihood for fewer strokes with PCI, especially in the first 30 days to 1 year (which in most cases is a clinically more important endpoint than MI, although the trial will not be powered to demonstrate a reduction in stroke), and the likely higher rate of subsequent unplanned revascularization for PCI.

2.7 STUDY SUCCESS

Study success is defined as passing the non-inferiority test of PCI to CABG on the primary endpoint of all cause death, MI or stroke (mRS \geq 1 and increase by \geq 1 from baseline) at 3 years. Detail of the test is specified in sections 2.5.1.

2.8 RANDOMIZATION AND BLINDING

Approximately 1,900 subjects will be enrolled in a 1:1 ratio to either PCI with the XIENCE stent or CABG treatment. Randomization will be stratified by the presence vs. absence of medically treated diabetes, SYNTAX ⁽⁴⁾ score <23 vs. \geq 23, and study center. A centralized randomization service will be used.

Randomization will be performed after informed consent has been obtained and all eligibility criteria have been confirmed. Once randomized, the subject is considered registered in the trial and analyzed as part of ITT population. Once randomization is completed and a treatment is assigned, crossover is not permitted.

This is an unblinded clinical study.

